4. SELECTION AND ENROLLMENT OF SUBJECTS

4.1. Inclusion Criteria

- 4.1.1. Diagnosis of glucose transporter type I deficiency (G1D), confirmed by clinical genotyping at a CLIA-certified laboratory or by PET scan.
- 4.1.2. Stable diet on either a modified Atkins diet or on no dietary therapy (i.e., no dietary therapy for 1 month).
- 4.1.3. Males and females 24 months to 35 years old, inclusive.

4.2. Exclusion Criteria

- 4.2.1. Subjects with evidence of independent, unrelated metabolic and/or genetic disease.
- 4.2.2. Subjects with a chronic gastrointestinal disorder, such as irritable bowel syndrome, Crohn's disease, or colitis that could increase the subject's risk of developing diarrhea or stomach pain.
- 4.2.3. Subjects with a BMI (body mass index) greater than or equal to 40.
- 4.2.4. Subjects currently on dietary therapy (i.e., ketogenic diet, medium chain triglyceride-supplemented diets, Atkins diet, and low glycemic index diet.).
- 4.2.5. Subjects with no evidence of abnormal EEG (spike-wave discharges).

- 4.2.6. Women who are pregnant or breast-feeding may not participate. Women who plan to become pregnant during the course of the study, or who are unwilling to use birth control to prevent pregnancy (including abstinence) may not participate. Females age 10 and over will be asked to provide a serum or urine sample for a pregnancy test via dipstick. Subjects will be asked to agree to abstinence or another form of birth control for the duration of the study.
- 4.2.7. Allergy/sensitivity to C7.
- 4.2.8. Previous use of triheptanoin in the past 1 month. Subjects who participate in Protocol 1 of this study are thus eligible.
- 4.2.9. Subjects exhibiting signs of dementia, or diagnosed with any degenerative brain disorder (such as Alzheimer's disease) that would confound assessment of cognitive changes, in the opinion of the investigator.
- 4.2.10. Active drug or alcohol use or dependence that, in the opinion of the investigator, would interfere with adherence to study requirements.
- 4.2.11. Inability or unwillingness of subject or legal guardian/representative to give written informed consent, or assent for children age 10-17.
- 4.2.12. Addition of a new antiseizure drug in the previous 3 months.

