Interventions and Duration

This is an open-label, single arm trial of orally-administered C7 in G1D. Subjects will replace a fixed percentage of their daily caloric intake (based on the results of Protocol 1) with C7 for 6 months, undergo full evaluation and discontinuation of treatment at a 6 month visit, and return for an off-treatment follow up visit 3 months after C7 oil discontinuation, for total duration of participation of 9 months. Subjects will undergo

treatment initiation on a 24-hour inpatient basis. During that 24-hr inpatient treatment initiation, subjects will have continuous EEG both to monitor for real-time seizure activity (for safety) and to determine EEG changes (secondary outcome) before, during, and after treatment initiation. Subjects will undergo clinical evaluation, comprehensive blood work, ataxia scale rating, EEG, and neuropsychological testing at baseline, 6 months, and 9 months.

Important: As described in the Proposal and in (1), C7 is always administered as a **replacement** (nor as a source of extra calories for an otherwise unchanged regular diet) to a fraction of the daily calories that are normally consumed by each subject via other nutrients. As such, there is **no caloric impact** of C7 (i.e., the calories that a subject will consume remain unchanged by the addition of C7 to the diet to replace other nutrients – predominantly fat).

Sample Size and Population

Forty-five subjects receiving no dietary therapy (i.e., consuming a normal diet) with a proven (genetically determined) G1D diagnosis will be enrolled. Subjects may be male or female, between the ages of 2 and 35 years old (N=15 per age group: 2 to 6, 7-11, and 12-35 years old), and must be willing to provide assent if they are of age 10-17. Subjects may be English or Spanish speaking. Subjects may be currently taking anticonvulsants or other medications. Subjects must agree not to change their dietary therapy during the trial without consulting with the study team. Subjects must have evidence of abnormal EEG in the last 36 months.

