5. STUDY INTERVENTIONS

5.1. Interventions, Administration, and Duration

5.1.1. Triheptanoin: A triglyceride oil containing three odd-carbon chain-length fatty acids (i.e., a triglyceride of 7-carbon heptanoic acid) manufactured for food applications. Triheptanoin will be taken 4 times per day (approximately every 6 hours: prior to breakfast, lunch and dinner and a mid-afternoon snack) by mouth. It is dosed 4 times per day, divided evenly. Subjects will receive supplementation at the maximum tolerable dose (MTD) determined in Protocol 1 (either 35%, 40%, or 45% of daily caloric intake). Subjects who experience acute gastrointestinal distress (nausea, mild stomach upset, mild diarrhea) may decrease the dose to 50% for two days, then increase the dose over the course of less than a week (in a manner similar to what is described in Protocol 1) until they reach the intended dose. Subjects who are unable to tolerate the maximum tolerable dose will be discontinued from the study. The oil

should be taken approximately one hour before meals, and will be mixed with fat-free, sugar-free yogurt or pudding for administration.

- 5.1.2. Forty-five subjects will be enrolled in a 6 month on/3 month off treatment trial of triheptanoin. Initiation of triheptanoin will be done in the Children's Medical Center Dallas Epilepsy Monitoring Unit.
- 5.1.3. Subjects will not be required to stop other medications. Subjects will be directed to maintain their usual medications, including rescue seizure medications, as necessary for the course of the study. Subjects may have any clinical medical records transferred back to their referring physician at completion of the study.

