5.3. Concomitant Interventions

- 5.3.1. Required Interventions: There are no additional required interventions.
- 5.3.2. Prohibited Interventions: Subjects are prohibited from starting or changing dietary therapy or other oil-based dietary modifications (including ketogenic diet or medium chain triglyceride therapy) while on study protocol. Subjects who feel this change is necessary will be withdrawn from the study for their own protection.
- 5.3.3. Precautionary interventions: [name] or M.D. co-investigator may direct subjects to adjust the dosing of their oil if necessary for tolerability. If subjects experience acute gastrointestinal distress by self-report during treatment initiation, the amount of oil administered will be decreased to 50% of the dose for 2 days, then gradually increased over less than a week until the desired dose is reached. Subjects who are unable to tolerate the maximum tolerable dose of oil will be discontinued from the trial. If subjects experience gastrointestinal distress during the 6 months of treatment (post treatment initiation), the amount of C7 oil will also be decreased as above. Subjects unable to tolerate a return to the required dose will be discontinued from the study. A dietitian will also be available to provide nutritional counseling for subjects who are having difficulties adjusting to the oil, as experience has shown that mixing the C7 oil with an emulsifier, such as yogurt, and other simple dietary interventions can effectively and permanently improve tolerability (based on our previous experience with G1D (1)).
- 5.3.4. Drug treatments during C7 consumption: G1D patients will generally not need to change any concomitant drug treatment as part of this study. Such changes may be initiated by outside local neurologists or by M.D. investigators in this study and prompted by increased seizure frequency or unexpected drug toxicity. While participants will be screened for a stable drug regimen (see Exclusion Criteria) and recognizing that changes in such therapy may occur, the following scenarios will be entertained:

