 - 5.3.4.1. No change in type of drug treatment is the planned study conduct. It is likely that this plan will be followed by all subjects because, in clinical practice, the withdrawal of an antiseizure drug on a given patient is usually evaluated only at 2-year intervals, which exceeds the duration of this Protocol. Modest (10-25% dose) changes will be allowed per standard clinical practice in rapidly growing (young) children, whose weight normally increases on a monthly basis. These children will thus continue to be treated per standard pediatric neurological practice.
 - 5.3.4.2. Addition of a new antiseizure drug. This will be prompted by increased seizures and is equivalent to C7 failure.

5.3.4.3. Discontinuation of an antiseizure drug. This will be prompted by drug adverse events and recorded as such (as outlined below). Such events are very unlikely in patients who have been receiving a stable drug regimen (see Exclusion Criteria).

5.4. Adherence Assessment: The coordinator will call subjects and families once a month to determine adherence (by self-report), remind subjects to go in for the month two lab draw if not already done, and assess amount of oil remaining, and will prompt and procure an answer to any questions that the family may have. If any subjects are having trouble as reported during a call, [name] or M.D. co-investigator will be notified and a written plan of action will be developed. Additionally, a nutritional consult will be completed to determine if the C7 dose is still correct. If the subject's caloric intake has changed significantly enough to require a change in the amount of C7 needed, the dietician will consult with PI or M.D. co-investigator, who will contact the family to provide directions for the dose change.

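### Section 5.3.4 relies on entry screening for a stable drug regimen, but exclusion 4.2.12 bars only a newly added antiseizure drug, so recent withdrawals or dose changes can bias the single-arm responder count in either direction

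*Combined protocol and SAP*

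**What the plan says.** **What Section 5 relies on.** Section 5.3.4 introduces its scenarios for drug changes with: "While participants will be screened for a stable drug regimen (see Exclusion Criteria) and recognizing that changes in such therapy may occur". Section 5.3.4.3, on stopping an antiseizure drug during the study, uses the same screening as reassurance: "Such events are very unlikely in patients who have been receiving a stable drug regimen (see Exclusion Criteria".

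**What Section 4 contains.** The one exclusion on recent drug history is 4.2.12: "Addition of a new antiseizure drug in the previous 3 months". The synopsis (Sample Size and Population) is permissive: "Subjects may be currently taking anticonvulsants or other medications". It sets no look-back period.

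**What applies after entry.** Section 5.1.3 says: "Subjects will be directed to maintain their usual medications, including rescue seizure medications, as necessary for the course of the study". Section 5.3.4.1 adds: "Modest (10-25% dose) changes will be allowed per standard clinical practice in rapidly growing (young) children". On a new antiseizure drug, Section 5.3.4.2 says: "This will be prompted by increased seizures and is equivalent to C7 failure". Section 5.3.4.3 has discontinuations recorded as adverse events and says nothing about how such a subject counts in the primary outcome.

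**What is analysed.** Section 9.1 defines a favourable outcome as a gain of at least 0.5 normative SD on the age group's attention measure. Section 9.3 tests 50% against 80% in each age group with a Simon two-stage rule. Section 9.5 estimates the responder proportion with an exact binomial interval and names no medication covariate, exclusion or sensitivity analysis.

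**The concern.** Section 5 cites a safeguard that Section 4 only partly supplies. Under 4.2 as written, a subject whose antiseizure drug was withdrawn, or whose dose was substantially changed, a week before Visit 1 is eligible.

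This matters because each subject is compared only with his or her own pre-oil baseline. The protocol itself says that attention is commonly impaired in seizure disorders, so a change in seizure treatment acts close to the measured construct. If its effect is still developing at baseline, part of it falls inside the comparison. It may then be credited to C7 or hide a C7 benefit. With 13 evaluable subjects per age group, one or two such subjects can decide a go/no-go recommendation.

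**Working it through.** **1. Does another passage close the gap?**

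| Place | Covers withdrawal or dose change before entry? |
|---|---|
| 4.1.2 (inclusion) | No: stable diet only |
| 4.2.10 | No: drug or alcohol use or dependence |
| 4.2.12 | No: addition of an antiseizure drug only |
| 5.1.3 | No: applies from entry onward |
| 5.3.2 | No: prohibits dietary changes only |
| 5.3.4.2 | No: additions during the study |
| 6.3.3 | Records current and past treatments, with no link to eligibility |
| 6.3.9 (Patient History Form) | Collected to control confounding, but not carried into 9.5 |
| 9.5 | No medication term or sensitivity analysis for the primary outcome |

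The gap stands.

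**2. Reproduce the stated design (Section 9.3).** The rule is to continue if at least 5 of 7 respond, and to pass if at least 9 of 13 respond in total. With X the stage 1 count (n = 7) and Y the stage 2 count (n = 6):

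P(go) = Σ over x = 5, 6, 7 of P(X = x) · P(Y ≥ 9 − x)

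- At p = 0.5: 0.1641 × 0.3438 + 0.0547 × 0.6562 + 0.0078 × 0.8906 = 0.0992 (stated type I error 0.1).
- At p = 0.8: 0.2753 × 0.9011 + 0.3670 × 0.9830 + 0.2097 × 0.9984 = 0.818 (stated power 80%).

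The plan's figures reproduce.

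**3. Let k of the 13 subjects have a different response probability q.** Both k and q are assumptions; neither is in the documents. The affected subjects fall at random into stage 1 or stage 2. For k = 2, the probability that j of them are in stage 1 is C(7, j) · C(6, 2 − j) / C(13, 2), which is 15/78, 42/78 and 21/78 for j = 0, 1, 2. The overall P(go) is the weighted mean of the exact P(go) for each j.

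| Others | Affected (q) | P(go), j = 0 | j = 1 | j = 2 | Weighted mean |
|---|---|---|---|---|---|
| 0.5 | 0.8 | 0.1421 | 0.1605 | 0.1764 | 0.161 |
| 0.5 | 0.2 | 0.0586 | 0.0507 | 0.0401 | 0.049 |
| 0.8 | 0.5 | 0.7613 | 0.7160 | 0.6480 | 0.706 |

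**4. Range over the number affected.**

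| Scenario | k = 0 | k = 1 | k = 2 | k = 3 |
|---|---|---|---|---|
| C7 inert, affected at 0.8 | 0.099 | 0.127 | 0.161 | 0.202 |
| C7 inert, affected at 0.2 | 0.099 | 0.071 | 0.049 | 0.033 |
| C7 works (0.8), affected at 0.5 | 0.818 | 0.766 | 0.706 | 0.641 |

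With two affected subjects and C7 inert, q = 0.7 gives 0.139 and q = 0.9 gives 0.185. One subject at 0.8 and one at 0.2 give about 0.093, close to no net effect.

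**5. Which comparison is exposed?** The schedule in Section 6.3.9 tests attention on Visit 1 Day 1 and Day 2, at 6 months and at 9 months. Section 9.1 places the 6-month responses among the other outcomes, while 9.2.1.1 claims benefit in both the acute and the long term. From Day 1 to Day 2 an earlier drug change has about one day to evolve; from baseline to Visit 2 it has six months.

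**The case against.** The strongest reply is that this is a loose cross-reference with an effect of unknown size.

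- **Direction.** A reader might infer that recent drug changes manufacture responders and so inflate false positives. The documents do not support that. Stopping or reducing an antiseizure drug could as easily worsen seizures and attention, and the second row of the range table shows the false-go chance falling. This stands: the point is bias of unknown sign.
- **Timing.** If the primary comparison is Day 1 to Day 2, exposure is slight. This stands in part, because 9.2.1.1 keeps the 6-month comparison in play.
- **Frequency.** Section 5.3.4.1 says that withdrawal is usually considered only at 2-year intervals, so a withdrawal just before entry should be uncommon. That is a fair point for withdrawals. It does not cover dose changes.
- **Other safeguards.** A reader might infer that the trial has no other way to separate drug from oil. That goes too far. Treatment history is recorded (6.3.3), a history form is collected to control confounding (6.3.9), and attention is retested 3 months off oil. That last contrast is ambiguous, since a C7 benefit might persist too. None of these enters the primary responder analysis as 9.5 is written.
- **Attention drugs.** A reader might also infer that the plan promises screening for newly started attention drugs. The documents never mention them, and the scenarios under 5.3.4 concern antiseizure drugs. Such drugs belong in a sensitivity analysis, not in the claimed mismatch.

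**Conclusion.** The mismatch is certain and can be read directly from the text: 5.3.4 and 5.3.4.3 claim entry stability that 4.2.12 does not deliver for withdrawals or dose changes of antiseizure drugs. Its effect on the trial is possible but not quantified. With two of 13 subjects affected, the false-go chance in one age group could be 0.161 or 0.049 instead of 0.099, and power could be 0.706 instead of 0.818. These figures rest on assumed response probabilities and an assumed number affected; they are illustrations, not estimates. The bias may run either way and bears mainly on the baseline-to-6-month comparison. The stated design and sample size are unaffected. The point is worth correcting because the primary decision rests on few subjects without a control arm and the correction is cheap.

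**What to change.** 1. **Reconcile 4.2.12 with 5.3.4.** Extend the existing 3-month window from addition to any change of antiseizure regimen. Exempt the growth-related changes described in 5.3.4.1, and allow re-screening once the window has passed. The investigators should set the clinical content. This concerns eligibility only and asks nobody to alter treatment.
2. **Add a sensitivity analysis to 9.5.** Using the treatment history already collected under 6.3.3, repeat the responder proportion and its exact interval with subjects who had a recent or on-study change in antiseizure or other attention-affecting drugs (a) excluded and (b) counted as non-responders. The two-stage rule itself stays as it is.

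Cost: amendment wording, one item in the screening history and a short addition to the analysis section. Some candidates would wait up to 3 months. Enrolment is planned at only 1-2 subjects a month, so the delay should be manageable, but the documents do not say how many candidates it would affect.

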4.3. Study Enrollment Procedures

4.3.1. Recruitment

[name] is the Director of the Rare Brain Disorders Program at UT Southwestern Medical Center and Children's Medical Center Dallas. This clinic currently provides care for approximately 100 confirmed G1D subjects from around the United States. [name] current subjects will be contacted by [name] to determine interest in participating in this research. Our experience has been that, due to the childhood manifestations of this disease, the chronic nature of symptoms, and the difficulty in finding effective treatments, these families and subjects are particularly eager for clinical trial opportunities. Our pilot study of G1D (1), which was conducted to establish the feasibility of a similar protocol as well as providing other preliminary data, recruited 14 subjects in 15 days and had to decline as many as twice that number of interested subjects who made contact just after recruitment was complete.

In addition, [name] maintains a strong collaborative relationship (Medical Advisory Board chair) with the Glut1 Deficiency Foundation, the leading community-based patient advocacy 501(c)(3) organization dedicated to supporting research in G1D (see Letter of Support). [name] is an invited speaker to their annual meeting, and the G1D Foundation has expressed its

willingness to support and promote our research efforts through their community boards and newsletters.

Information regarding the trial will also be posted on the ClinicalTrials.gov and UT Southwestern websites, the latter of which includes a searchable database for current trials ongoing at UT Southwestern.

An additional recruitment tool is our web-based, patient-generated G1D patient registry (www.G1DRegistry.org). The registry is an IRB-approved, HIPAA-compliant comprehensive, inclusive questionnaire that captures all relevant aspects of G1D natural history and therapies. The registry, which has been accessible for 1 ½ years now, is housed in the UT Southwestern servers that contain the medical center medical records and currently has over 200 unique enrollees.

4.3.2 Screening Log and Enrollment

We anticipate enrolling approximately 1-2 subject(s) every month for 44 months (months 14-44). Because this study is resource intensive due to the inpatient stay, enrollment at a rate greater than 1-2 per month is not feasible for personnel and resource availability. This enrollment rate allows for flexibility in scheduling the Epilepsy Monitoring Unit (EMU) with these research patients.

A screening log will be maintained in an Excel spreadsheet, documenting how subjects learned about the trial ([name], community group, clinicaltrials.gov, etc.), who referred them to the trial, the reasons for ineligibility (if applicable), and the reasons for nonparticipation of eligible subjects. The research coordinator will meet with [name] at the end of each clinic day to confirm eligible and ineligible subjects seen during the day. The research coordinator will be responsible for screening the designated secure UT Southwestern email account, contacting interested subjects, and logging which subjects qualify and which subjects do not and why. All of these procedures are in place and have been successfully used by us for (1).

Enrollment will open in month 14, although screening will begin prior to this month in order to schedule appointments immediately. We anticipate reaching 25% enrollment for this study in month 20, 50% enrollment in month 27, 75% enrollment in month 35, and 100% enrollment in month 44.

Recruitment will be monitored monthly. If recruitment goals fail to be met within the first 6 months of opening enrollment, the recruitment log will be analyzed to clarify the reasons for lack of enrollment, and these reasons will be addressed if possible. In our experience, this population is eager for research studies and very willing to participate, even traveling from several states away and Canada to participate in research.

If we have not met recruitment goals, we have several steps in place to improve recruitment.

1. We will utilize our G1D Registry, which includes a patient-agreed clause to inform registered patients about clinical research, and reach out these patients if they have not been enrolled. This process will take approximately 1-2 weeks, and we will re-evaluate recruitment, based on scheduled visits, after 4 weeks.
2. If recruitment is still lagging, or we have exhausted available patients in the registry, we will work with the Glut1 Deficiency Foundation. Per the FOA, researchers are encouraged to work with and engage patient groups. We have worked with the Glut1 Deficiency Foundation in various capacities over the past several years and maintain an excellent working relationship with them (See Letter of Support), including making their broad patient base regularly aware of our research. The Glut1 Deficiency Foundation will send an email to members with information regarding the trial, and encourage interested families to contact us if desired. This process will take 1-2 weeks, and recruitment will be re-evaluated after 4 weeks, based on scheduled visits.
3. Finally, if we still experience a lack of patients, we will reach out to the G1D Research Consortium (G1DRC; which is not contributing support letters because the Consortium is not part of this proposal), which we have established for the broad purpose of clinical investigation and patient information. There are currently 10 U.S. institutions in the consortium, which cover virtually all densely populated areas of the U.S. The relationship with Consortium members is excellent, as, even before the Consortium was formed, members had previously referred to us a total of 36 G1D patients for specialized neurological consultation.

In addition, if enrollment is slower than anticipated, it is within the scope of this research to allow an additional 6 months to enroll (months 45-50). See Protocol Timeline below.

Protocol Timeline

	Q2-Q3 2015	Q4 2015	Q1 2016	Q2 2016	Q3 2016	Q4 2016	Q1 2017	Q2 2017	Q3 2017	Q4 2017	Q1 2018	Q2 2018	Q3 2018	Q4 2018	Q1 2019	Q2 2019	Q3 2019	Q4 2019	Q1 2020	Q2 2020	Q3 2020
Pre-Award																					
Team Assembly																					
Team Training																					
IRB Approval																					
Specific Aim 1																					
Enrollment																					
Specific Aim 2																					
Enrollment																					
6 mo Follow up																					
9 mo follow up																					
Specific Aim 3																					
Enrollment																					
Data analyses																					
Data write up																					
Publication submission																					

